## **Abstract**

Nearly 30 million Americans have type 2 diabetes (T2DM), a disorder with serious health consequences such as cardiovascular and renal disease. Almost 90 million more have prediabetes, with estimates of 8 million undiagnosed (CDC, National Diabetes Statistics Report). Insulin resistance (IR) is a precursor to prediabetes and T2DM (NIDDK, Insulin resistance and prediabetes). There is evidence of IR in those with short sleep [normal weight (Matthews et al., 2012); obese (Liu, Kushida, & Reaven, 2013)]. The risk for developing diabetes in persons with difficulty in maintaining sleep is 1.84 times the risk of diabetes in those who do not have sleep issues which is very similar to the relative risk detected from another commonly recognized risk factor-- family history of diabetes (1.7-2.3) (Reutrakul & Van Cauter, 2014). For this pilot study we will recruit 20 young adults, accounting for attrition, age 18-25 years who have elevated HOMA-IR (based on established cut points), short sleep duration (< 7 hrs./night) and obesity (BMI  $\geq$  30) (another risk factor for IR), and use a two-group, pre-test/post-test experimental design including objective actigraphy data for sleep. The specific aims are to: 1) evaluate the feasibility and acceptability of a tailored intervention to extend sleep duration (SLEEP-Extend), 2) determine changes in sleep duration after SLEEP-Extend intervention, 3) evaluate IR levels before and after SLEEP-Extend, and 4) explore the potential mediators of diet and physical activity between sleep duration and IR. Screening data will include measures of sleep duration, age, IR and BMI. After enrollment, baseline data will include pre-test of sleep hygiene knowledge, self-report measures of diet and physical activity as well as one week of objective monitoring of sleep using actigraphy. After all baseline data are collected, participants will be randomly assigned to group. The SLEEP-Extend intervention group will receive sleep hygiene education and instructions to increase time in bed by one hour total each night for an additional 4 weeks. The attention control group will receive education on safety practices in an urban environment. Both groups will receive the sleep hygiene post-test immediately after the intervention, and they will continue with actigraphy monitoring for 4 weeks. After the 4-week intervention period, both groups will have measures of IR, BMI, final post-test of sleep hygiene knowledge, self-reported diet and physical activity, and an exit interview, and actigraphy data will be downloaded. This study will examine whether an intervention to extend sleep will result in behavior change to increase sleep duration and improve IR.

## **Introduction and Background**

Type 2 diabetes (T2DM) is an increasing public health concern despite national efforts to reduce incidence as well as risk (ADA, Statistics about diabetes). Almost 30 million Americans have diabetes and nearly 90 million more have prediabetes (CDC, National Diabetes Statistics Report), all of which costs the U.S. approximately \$245 billion each year (ADA, Statistics about diabetes). Once predominantly associated with middle-aged and older adults, the incidence of this disease among children and young adults has increased dramatically (ADA, Statistics about diabetes). According to the Centers for Disease Control and Prevention the incidence of diabetes in persons 0-44 years old increased 167% from 1980 to 2011 (CDC, Rate of 100 per civilian). In fact, it is estimated that if T2DM continues to increase at the present rate, the number of people under 20 years of age with T2DM could increase by up to 49% by 2050 (Imperatore, et al, 2012). In 2010, diabetes was the 7th leading cause of death (ADA, Statistics about diabetes), and this disorder can lead to serious cardiovascular, renal, and neurological problems. Many risk factors for T2DM are preventable (ADA, Are you at risk?), and most interventions aimed at preventing or delaying the onset of T2DM focus on weight loss since obesity is considered a major risk factor for developing insulin resistance (IR; a precursor to prediabetes and T2DM) and T2DM. The role of insufficient (short) sleep duration is often overlooked, even though *the relative risk for developing diabetes in persons with short sleep duration is 1.28 and those with difficulty maintaining sleep is 1.84 which is nearly that of the relative risk for diabetes in persons with a family history of diabetes (1.7-2.3)* (Reutrakul & Van Cauter, 2014). Recent guidelines published by the National

Sleep Foundation (NSF) suggest that young adults 18-25 years obtain 7-9 hours of sleep per night (NSF, NSF recommends new sleep times). Insufficient sleep and sleep deprivation are becoming more common in young adults (Petrov et al., 2014), and just under 1/3 of the individuals aged 18-24 years of age surveyed in 2009 complained of insufficient sleep  $\geq 14$  days in the past 30 days (Liu, Y. et al, 2013). A Gallop poll reported even more alarming numbers with 49% of the individuals polled between the ages of 18 and 29 reporting less than 6 hours of sleep/night (Jones, 2013). This finding is particularly concerning since *short sleep duration was identified as an independent risk factor for the development of IR and T2DM* (Reutrakul & Van Cauter, 2014). Our goal is to delay the onset of T2DM; thus, we are intervening with young adults---an age where primary prevention efforts may be most effective.

Evidence for the mechanism linking short sleep duration (< 6 hrs./night) with insulin resistance (IR) includes increased sympathetic activity, altered rhythm of cortisol secretion and increased concentration of inflammatory markers (Reutrakul & Van Cauter, 2014). Additionally, several experiments have demonstrated that sleep restriction alters leptin, and leptin-to-ghrelin (hormones that regulate appetite) ratios in healthy young adults, and hunger and appetite are reported to increase with sleep restriction (Spiegel et al, 2005). A few studies examining sleep-restricted individuals found that aspects of neurological and cognitive function, such as visuospatial processing, daytime alertness, and mood were improved after sleep was extended (Dewald-Kaufmann, Oort, & Meijer, 2013; Gumenyuk et al., 2011; Kamdar, et al., 2004). The majority of these studies only included a short time frame for the sleep intervention, and none of those studies included examination of IR. Our SLEEP-Extend intervention will occur over a 4-week period. From their regression model, Matthews et al, (2012) estimated that, based on only one additional hour of sleep, healthy adolescent boys with short sleep (< 6 hrs./night) would have an almost 9% improvement in their IR levels. One study has examined the effects of an intervention to extend sleep on glucose metabolism in healthy adults (not obese nor with pre-determined IR levels) ages 20-50 years old with less than 7 hours sleep/night (they extended sleep by one hour total each night over 6 weeks) (Leproult et al, 2015). Although there were no significant changes in IR, there were significant increases in sleep duration as well as improvements in insulin sensitivity in these healthy individuals. This study underscores the achievability of getting sleep-deprived individuals to extend their sleep duration. Our study differs from Leproult and colleagues (2015) in that we will examine individuals with IR. Our recently completed preliminary study found that almost 20% of young adults (N=32) with short sleep had IR (based on established cut points). Out of those with IR, 50% were obese (BMI  $\geq 30$ ), and this is supported by other studies with similar results (Blanco et al., 2012). We feel that, compared to Leproult's study, we will implement a stronger study design with SLEEP-Extend by including only individuals with IR and by adding a control group.

Despite increased awareness of T2DM and its risk factors, the incidence of this disorder is growing, especially in younger adults. Short sleep duration has been identified as an independent risk factor for IR and T2DM; however, few lay persons are aware of this finding. Innovative and easily implemented primary prevention efforts are needed to prevent progression of disease in those with IR, a precursor to T2DM, and addressing sleep deprivation may be one effective method. We know that development of T2DM is complex and can involve multiple factors. Our participants will have the T2DM risk factors of IR, obesity and short sleep duration, but we are focusing our attention on extending sleep duration while not intervening with nutrition, physical activity and body weight in order to better evaluate the efficacy of our sleep intervention. If our results show this tailored sleep intervention (SLEEP-Extend) is feasible and does extend sleep duration as well as provide preliminary evidence of improved IR levels in sleep-deprived young adults at risk for T2DM, then we will have a foundation for a larger study to test the efficacy of SLEEP-Extend. Additionally, this initial SLEEP-Extend intervention will be a relatively low-cost approach to reduce this one risk factor (short sleep) of T2DM. The study will provide evidence of impact in intervening with sleep duration to improve metabolic function. Only one study has explored sleep extension as an intervention for short sleep duration and studied the effects on

glucose metabolism, and no sleep extension studies were found in a population at risk for T2DM. Based on the lack of evidence, little is known about how extending sleep will impact IR.

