
## **Study Methods**

**Design:** A two-group, pre-test/post-test experimental design will be used to examine the feasibility and estimate the effects of a sleep intervention (SLEEP-Extend) designed to extend sleep duration in obese, young adults with short sleep and IR. Participants will wear actigraphy watches for one week of baseline sleep data and for an additional four weeks during the intervention.

**Sample/Setting:** We will recruit from Emory Hospital and Emory affiliated hospitals (Children's Healthcare of Atlanta, Emory St. Joseph's, Emory Johns Creek, Emory Midtown) through nursing staff email listservs as well as through flyers on Emory University campus and in areas that might attract young adults, through course web announcements, listservs for student emails and through social media, 20 obese individuals age 18-25 years old with short sleep (duration less than 7hrs./night) and evidence of IR [HOMA-IR levels  $\geq 2.1$  using serum sample (Esteghamati et al., 2010)] (See Timeline). We want to ensure 10 participants are in both groups; therefore, based on our previous experience recruiting from this age group, we will recruit individuals to give us a final N=20 (10 in each group).

Inclusion criteria: 1) Age 18-25 years old, 2) Self-report short sleep, 3) BMI  $\geq 30$  (the World Health Organization's classification of being obese, 4) IR determined by serum analysis, 5) Be willing to extend time in bed (See intervention below) by one hour total per night, and 6) Read and speak English.

Exclusion criteria (all self-report): 1) Night shift workers (circadian disruption can alter glucose and insulin levels), 2) Diagnosed sleep disorder (e.g., sleep apnea, restless leg syndrome,) which may impact glucose, insulin, and other hormones, 3) Medical diagnosis of diabetes or pre-diabetes, 4) Pregnant or lactating women or history of gestational diabetes, 5) Actively or intentionally trying to lose or gain weight (alteration of glucose metabolism/insulin secretion), 6) Hospitalization in past 3 months for medical or psychiatric condition, or 7) Major chronic disease (e.g., cancer, Lupus). The 5-week study will be conducted during the middle of the semester when the longer holidays and final exams do not occur.

1. Data samples will not be saved/banked or archived for future use.

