receive \$20 after one week of baseline data. At the end of the study, all participants will receive an additional \$30, a certificate of appreciation and a booklet on Healthy Sleep (NHLBI, 2011). Any participants that are noted to have additional risk factors for T2DM will be provided educational material on reducing T2DM risk factors and the suggestion made to follow up with a physician. After serum blood values are analyzed, all participants will be sent a letter with their glucose, insulin and HOMA-IR information along with a description of these values and recommendation for physician follow up. The principal investigator is a registered nurse who will collect the data and administer the sleep intervention. Standard universal precautions will be used during blood draws. Additionally, a GRA, also a registered nurse, will assist with data collection.

**Sample size:** A target sample size of 10 in the SLEEP-Extend group and 10 in the control will be used for this feasibility study (accounting for 20% attrition) given the need for a serum blood test as part of screening a number of participants to meet strict eligibility criteria. Participants will be randomly assigned to either the control or SLEEP-Extend group using a table of random numbers.

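### Improved IR is listed among the results that would support a larger trial, but 8 to 10 completers per arm separate the cited 9% effect poorly from no effect

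*Combined protocol and SAP*

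**What the plan says.** The last paragraph of Introduction and Background says what the pilot must show to justify a larger efficacy study. Feasibility and longer sleep come first, and the sentence then continues "as well as provide preliminary evidence of improved IR levels in sleep-deprived young adults at risk for T2DM, then we will have a foundation". No other part of the document says what would justify going on. The IR element has no comparator (before versus after, or SLEEP-Extend versus control), no threshold and no confidence level. The same paragraph goes on to say that the study will supply evidence on metabolic function.

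The Design paragraph of Study Methods sets a more modest purpose: to "examine the feasibility and estimate the effects of a sleep intervention". The Sample size paragraph justifies the number by the burden of screening: "A target sample size of 10 in the SLEEP-Extend group and 10 in the control will be used for this feasibility study". It adds that this number already allows for a 20% loss of participants. The Sample/Setting paragraph reads differently: "we will recruit individuals to give us a final N=20 (10 in each group").

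The only IR effect size is in the Introduction. A regression in healthy adolescent boys with short sleep implied that, with one more hour of sleep, they "would have an almost 9% improvement in their IR levels". The one earlier extension study described in detail is reported as showing no significant change in IR, although insulin sensitivity improved.

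In Objectives, Aim 3 looks at IR before and after SLEEP-Extend, and H2 compares the proportions of each arm whose IR falls. Outcome Measures takes the baseline blood sample at the screening visit, and entry requires HOMA-IR of at least 2.1 on that sample.

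**The concern.** A reader of the final report will ask whether the pilot met its stated test. If the IR element is met or missed largely by chance, it adds little to that judgement. A favourable direction could be reported as early evidence of metabolic benefit, and an unfavourable one could count against an intervention that is workable and lengthens sleep. Aim 3 invites the weakest version, a before/after comparison in the treated arm. Because participants are selected on the same HOMA-IR value that serves as baseline, some fall at week 4 is expected from regression to the mean alone. A sound between-arm analysis removes that bias but not the imprecision, so the problem remains even if IR is analysed well.

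**Working it through.** **1. Completers per arm.** If the 20% attrition is already inside the 10, then 10 × (1 − 0.20) = 8 complete. If 10 is the final number, 10 complete, and 10 / (1 − 0.20) = 12.5, so 13 per arm must enrol. Both 8 and 10 are carried forward. The plan gives no alpha, power, SD or IR planning effect, so there is no power calculation to reproduce.

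**2. Effect.** A 9% fall is ln(0.91) = −0.094 on the log scale.

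**3. Simulation of the IR element.** Log HOMA-IR at a visit is a person's true level plus visit error. The documents give no spread, so these values are assumptions:
- between-person SD 0.45
- within-person (visit error) SD 0.20 or 0.30
- median of the screened population 2.1 or 2.8

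From the plan: enrolment if the screening value is at least 2.1, that value used as baseline, and 8 or 10 per arm. Ranges run over all scenarios.

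| Reading of the IR element | Met with no effect | Met with a true 9% effect |
|---|---|---|
| Mean fall within SLEEP-Extend | 65-86% | 89-97% |
| Baseline-adjusted between-arm difference favourable | about 50% | 67-78% |
| H2 in direction (more participants with a fall in SLEEP-Extend) | 38-43% | 53-65% |
| Adjusted difference favourable and significant, two-sided 0.05 | 2-3% | 6-11% |

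The first row exceeds 50% with no effect because of selection on the baseline value. The third is below 50% because ties count as not met.

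**4. Closed-form check on the Analysis Plan's own scale, percent change.** The SD of percent change is assumed to be 20 to 40 points. This fits step 3: the SD of a log change is √2 × 0.20 = 0.28 to √2 × 0.30 = 0.42. For a 9-point difference, SE = SD × √(2/n), P(favourable) = Φ(9/SE), and the 95% CI half-width is t × SE. Worked case, SD 30 and n = 10: SE = 30 × √0.2 = 13.4, Φ(9/13.4) = Φ(0.67) = 75%, half-width 2.10 × 13.4 = 28 points.

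| SD | P(favourable), n = 8 / 10 | Power, two-sided 0.05 | 95% CI half-width (points) | n per arm for 80% power |
|---|---|---|---|---|
| 20 | 82% / 84% | 13% / 16% | 21 / 19 | 78 |
| 30 | 73% / 75% | 9% / 10% | 32 / 28 | 175 |
| 40 | 67% / 69% | 7% / 8% | 43 / 38 | 311 |

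The last column is 2 × (1.96 + 0.84)² × SD² / 9². The half-width is at least twice the cited effect in every row.

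**5. H2 as a test.** Even 9 of 10 decreasing against 5 of 10 gives a Fisher exact p of 0.14.

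**6. Where separation improves.** With a true effect of 20% (an illustration), the adjusted difference is favourable 87-96% of the time, against 50% with no effect. With a within-person SD of 0.10, a 9% effect gives a favourable difference 90-94% of the time and a significant one 22-31%. On the percent-change scale, an SD of 10 points gives 39% power with 8 per arm and 48% with 10.

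**The case against.** The strongest reply is that the plan contains no decision rule. The sentence is Introduction prose and says *if*, not *only if*. A reader might infer that a feasible, sleep-lengthening intervention without an IR signal would be abandoned, or that the whole decision rests on noise. The text supports neither: it states a sufficient set of findings, and feasibility and sleep extension count as well. This part of the reply stands. What remains is that nothing else in the document defines success, and the sentence names IR as one of three elements.

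A reader might also infer that every directional reading is met at least half the time with no effect. H2 in direction is not: it is met about 38-43% of the time. Nor does the Design paragraph conflict with the Introduction, since estimating effects is compatible with looking for preliminary evidence.

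The benchmark is also open to challenge. The 9% comes from healthy adolescent boys and is not a planning value for obese young adults with elevated HOMA-IR. One consent-section instruction allows more than one extra hour in bed, and Alternative Strategies cites an unpublished report of reduced IR in obese adults. A larger effect is possible and would be separated better. The SD is assumed. These points limit the size of the claim, but the plan offers neither a larger effect nor a smaller SD to set against it.

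Lastly, fixed thresholds in place of IR can misfire too. If retention were exactly the planned 80%, the chance of keeping at least 16 of 20 is the binomial sum over k = 16 to 20 of C(20,k) × 0.8^k × 0.2^(20−k) = 63%, so a study performing as planned would fail that rule 37% of the time. Any threshold therefore needs its pass rate checked first.

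**Conclusion.** The concern holds in a limited form. At 8 to 10 completers per arm, the IR element discriminates poorly between the one cited effect and none. A favourable adjusted difference moves only from about 50% to 67-78%, H2 in direction from 38-43% to 53-65%, and significance from 2-3% to 6-11%. A before/after fall in SLEEP-Extend is the least informative reading, since it appears about 65-86% of the time with no effect.

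These figures rest on a within-person SD of log HOMA-IR of 0.20 to 0.30, a between-person SD of 0.45, a screened median of 2.1 to 2.8 and a true effect of 9%. An effect near 20% or an SD near 0.10 would change the picture. The small sample is not itself a fault in a feasibility pilot. The weakness lies in listing an IR signal among the results that would justify the next trial. A wording change is worth making because it is cheap and guards against claiming a metabolic benefit that chance or regression to the mean could produce.

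**What to change.** In the Introduction, reword the sentence so that support for a larger trial rests on feasibility, acceptability, adherence and the baseline-adjusted between-arm difference in actigraphic sleep duration. The sponsor should choose the thresholds and check how often each would be passed under plausible good and poor performance before fixing them. The number behind any retention threshold also needs settling, by saying whether 10 per arm is enrolled or completed.

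In the Analysis Plan, report IR as the between-arm ratio of week-4 HOMA-IR, adjusted for baseline on the log scale, with its 95% CI. State that it is for planning the larger trial, is not evidence for or against efficacy, and does not by itself decide progression.

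This needs no new data, visits or participants. The one cost is that the pilot can no longer claim improved IR as a success criterion.

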## **Objectives**

**Aims:** The aims for this pilot study of young adults ages 18-25 years old with IR (based on established cut points), short sleep (< 7 hours/night) and obesity (BMI  $\geq$  30) are to: 1) evaluate the feasibility and acceptability of a tailored intervention to extend sleep duration (SLEEP-Extend), 2) determine changes in sleep duration after SLEEP-Extend intervention, 3) evaluate IR levels before and after SLEEP-Extend, and 4) explore the potential mediators of diet and physical activity between sleep duration and IR. Our hypotheses are: H1: Individuals undergoing SLEEP-Extend will have longer sleep duration and increased knowledge of sleep hygiene post-intervention compared to controls and, H2: A greater proportion of the SLEEP-Extend group will have a decrease in IR compared to the control group.

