### **Outcome Measures:**

**BMI and baseline blood samples will be obtained at the screening visit.** All other measures will be assessed at the baseline visit and at the end of the 4-week intervention period except for the following: 1) Actigraphy watch will be worn continuously, and daily sleep diary completed for the entire study period, 2) The sleep hygiene pre/post-test and safety pre/post-test (control group only) will be given prior to intervention, immediately post intervention and at end of 4-week intervention period (3 time points), 3) Participant characteristics questionnaire only at baseline, and 4) Both groups will receive the exit survey at end of 4 week intervention period. **Insulin Resistance:** A) Glucose and insulin levels will be measured from fasting serum samples. B) Insulin Resistance will be calculated from the measured glucose and insulin levels using standard formulas. Briefly, serum samples will be collected via venipuncture and analyzed at Cardiovascular Specialty Laboratories, Inc (Atlanta, GA) using standard laboratory approaches with calibrated equipment (See letters of cooperation, from [name] and [name]). These two values will be used to calculate the homeostatic model assessment of insulin resistance (HOMA-IR; blood glucose level X insulin level, divided by 22.5). Elevated values indicate IR. A cutoff score of HOMA-IR < 2.1 as normal and HOMA-IR  $\geq$  2.1 as elevated (evidence of IR) will be used as determined in non-diabetics (Esteghamati et al., 2010). **Sleep Duration:** Using wrist actigraphy (Motionlogger, AMI, Ardsley, NY) along with a sleep diary (required to help validate and score actigraphy data; Martin & Hakim, 2011), we will objectively monitor each participant's 24-hour sleep-wake cycle to obtain average sleep duration (total sleep time) for one week (baseline) prior to random assignment to group and will continue monitoring during the 4 week intervention period. All participants wear the device (looks like a watch) on the wrist continuously for a total of 5 weeks (1 week for baseline sleep and 4 weeks of intervention period), except while bathing or swimming. Leproult and colleagues (2015) had success with adults wearing a wrist actigraph continuously for a total of 8 weeks. This device contains a light sensor that stores activity counts in 1-minute epochs and will detect the onset and offset of sleep using concurrent data from sleep diaries (Buysse et al., 2008; Morgenthaler et al., 2007). The Motionlogger was successfully validated against polysomnography on dimensions of sleep patterns: sleep onset latency, wake time after sleep onset, total sleep time (sleep duration), and sleep efficiency percentage (Cole et al., 1992). Data for each sleep component will be averaged over the 7 days for each week of the protocol (e.g. average sleep efficiency percentage, average total sleep duration) for analysis. Actigraphy has been compared to polysomnography to detect sleep and wakefulness and found to have a sensitivity of .965 and accuracy of .863 (Marino et al., 2013). The sleep diary is necessary to record data to help interpret actigraphy data (time in bed, time awake, and anything that occurs during the night such as waking up in the middle of the night). Participants in the SLEEP-Extend group will also use a daily sleep diary to record any sleep hygiene practices they use. Participants in the control group will use the same daily sleep diary as the SLEEP-Extend group with the difference of recording any safety practices used rather than recording sleep hygiene practices used. **Sleep Hygiene Knowledge:** To assess

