### **PROCEDURES:**

For interested participants, initial screening on the telephone for age, average sleep duration, and BMI will be done and if eligible, an appointment will be set and instructions for fasting (participant will be instructed to not eat or drink anything for 8 hours) for the screening visit (Visit #1). At Visit #1 we will obtain written informed consent that will include information on screening process: eligibility of IR (from blood sample) and height and weight measures will be obtained for BMI. Blood samples will be analyzed within one week. If HOMA-IR level is elevated in these obese individuals with short sleep, then they will be contacted and 2 additional appointments will be made. If they do not have elevated HOMA-IR levels, the researcher will call and thank them for their interest and let them know they are not eligible. Visit #2, baseline (BL) visit, will be within 2 weeks of obtaining initial blood result and consent will be confirmed (for enrollment in the study) and other BL data will be collected. Also, participants will be given a sleep diary to complete and an actigraphy watch to wear for one week for BL sleep assessment. During visit #3 (intervention visit) which is one week after BL visit, the BL actigraphy data will be downloaded and the participant instructed to continue to wear the watch for 4 more weeks. Randomization to groups will occur, and each group will receive the appropriate intervention content for the group. Immediately after the intervention, the appropriate knowledge post-test will be given according to assigned group. The SLEEP-Extend group will decide on when they are able to extend their TIB. After 2 more weeks both groups will receive a telephone call to reinforce content and answer questions about extending TIB and sleep hygiene for SLEEP-Extend group and safety information in the control group. At this telephone call the final appointment will be set for 2 weeks later and for a reminder to come in fasting. Visit #4 is the at the end of the 4-week intervention period, and data collection will include drawing of blood samples, downloading of actigraphy data with return of the watch and daily sleep diary and completing responses to standard questionnaires. To strengthen the design, we have made time spent with both groups similar throughout the study. All participants will

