### **Analysis Plan**

Data analysis will include descriptive statistics to characterize the sample and inferential statistics to compare study variables. Sleep characteristics will be expressed as percent change from beginning to end and analyzed with repeat measures ANOVA. Blood levels will also be expressed as percent change from baseline to last draw. Correlational analysis will be used with sleep variables and IR. Regression analysis including components of sleep, BMI, dietary and physical activity will be conducted to examine the association of sleep factors and IR. Responses to the exit interview questions will be content coded and interrater reliability assessed.

- 3. Data and Safety Monitoring and Reporting: If there is an adverse or reportable event, the IRB will be notified promptly via the eIRB reportable event form. Also, the event will be documented in a tracking log. The sponsor does not require reporting above and beyond Emory IRB reporting requirements. This study does not include more than minimal risk; however, the PI will periodically review documentation to ensure accuracy and completeness.

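### H2 reduces insulin resistance to any decrease, and the Analysis Plan specifies no between-arm analysis of it; a baseline-adjusted group comparison would use the same blood draws far better

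*Combined protocol and SAP*

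**What the plan says.** In the Objectives, the third aim is to "evaluate IR levels before and after SLEEP-Extend", which names no comparison group. The matching hypothesis does name one: "H2: A greater proportion of the SLEEP-Extend group will have a decrease in IR compared to the control group". No minimum size of decrease is set.

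Under Outcome Measures, "BMI and baseline blood samples will be obtained at the screening visit". The entry threshold is in the same section: "A cutoff score of HOMA-IR < 2.1 as normal and HOMA-IR" at or above 2.1 as elevated. Procedures then applies the threshold to that draw: "If HOMA-IR level is elevated in these obese individuals with short sleep, then they will be contacted and 2 additional appointments will be made". The visit details repeat the 2.1 requirement. No second draw before randomisation is described.

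The Analysis Plan says "Blood levels will also be expressed as percent change from baseline to last draw" and "Correlational analysis will be used with sleep variables and IR". It adds a regression of IR on sleep components, BMI, diet and physical activity; randomised group is not among the listed terms. Repeated-measures ANOVA is attached to sleep characteristics only. A general opening sentence promises inferential statistics to compare study variables, without naming an outcome, contrast or test.

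The only effect size for IR is in the Introduction and Background: a published regression model estimated that healthy adolescent boys with short sleep, given one more hour, "would have an almost 9% improvement in their IR levels".

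**The concern.** Two weaknesses meet on the trial's metabolic outcome.

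First, H2 splits a continuous measurement at zero change, so a 1% fall counts the same as a 40% fall. With 10 per arm that loss of information is expensive.

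Second, the hypothesis implies a group comparison, but the Analysis Plan does not say how it will be made for IR. What it does specify, percent change from baseline, starts from a value selected for being high. If that change is reported by arm without a contrast, or if Aim 3 is answered as worded, regression to the mean could pass for improvement.

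The Introduction says that preliminary evidence of improved IR would help found a larger study. That evidence should be a between-arm estimate, which the plan does not currently specify.

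**Working it through.** The plan states no alpha, power, effect size or SD, so there is no power figure to reproduce.

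**Inputs from the protocol:** 10 per arm, described as allowing for 20% attrition (Sample size); threshold 2.1; cited effect about 9%.

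**Assumptions, not in the protocol:** two-sided alpha 0.05; log HOMA-IR SD 0.5-0.6; test-retest ICC 0.6-0.8; geometric mean (GM) before selection 2.5-3.5. The central case is GM 3.0, SD 0.55, ICC 0.7.

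**1. Regression to the mean with no effect.** Let z = (ln 2.1 - ln GM)/SD, and let λ be the normal density at z divided by the upper tail probability beyond z. The expected fall in geometric mean is 1 - exp[-(1 - ICC) × SD × λ].
- Central: z = (0.742 - 1.099)/0.55 = -0.65, λ = 0.436. Fall = 1 - exp(-0.3 × 0.55 × 0.436) = 6.9%.
- Smallest (GM 3.5, SD 0.5, ICC 0.8): λ = 0.280. Fall = 1 - exp(-0.2 × 0.5 × 0.280) = 2.8%.
- Largest (GM 2.5, SD 0.6, ICC 0.6): λ = 0.623. Fall = 1 - exp(-0.4 × 0.6 × 0.623) = 13.9%.

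So the range is about 3-14%, and it includes the cited 9%. By simulation, 54-61% of participants decrease with no effect, against 50% without selection. A true 9% effect moves this only to 63-69%.

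**2. Ceiling on H2.** This step needs no HOMA-IR assumption, only that Fisher's exact test is used.
- 10/10 v 6/10: p = 2 × C(10,6)/C(20,16) = 2 × 210/4845 = 0.087.
- 8/8 v 4/8: p = 2 × C(8,4)/C(16,12) = 2 × 70/1820 = 0.077.

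Once 6 of 10 controls decrease (or 4 of 8, if 20% of 10 drop out), even a perfect result in SLEEP-Extend is not significant. Under step 1, six or more of 10 controls decrease with probability about 0.47-0.67.

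**3. Power at 10 per arm, central case, by simulation.**

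| True reduction | H2 proportion, Fisher | t-test on percent change | ANCOVA on log HOMA-IR |
|---|---|---|---|
| 9% | 2% | about 7% | about 8% |
| 30% | 13% | 42% | 46% |
| 40% | 23% | 71% | 76% |

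Most of the gain comes from not dichotomising; the choice between the last two columns matters little.

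**4. Sensitivity to other assumptions.** Take a source median of 1.5-3.0, between-person log SD 0.5 and within-person log SD 0.15-0.30. The null fall is then 2-17%, with 53-68% decreasing. Fisher power is 2-4% at a 9% reduction and 8-40% at 30%. ANCOVA power is 8-17% and 52-97%, by a normal approximation that is slightly optimistic at this size. The ordering is unchanged; the absolute values depend heavily on the assumed variability.

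**5. Precision of the ANCOVA estimate.** The residual SD is SD × √(1 - ICC²), and the half-width on the log scale is 2.11 × residual SD × √(2/10), with 17 df.
- SD 0.5, ICC 0.8: residual SD 0.30, half-width 0.283, interval ×0.75 to ×1.33.
- SD 0.6, ICC 0.6: residual SD 0.48, half-width 0.453, interval ×0.64 to ×1.57. With chance baseline imbalance this is roughly ×0.63 to ×1.58.

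**The case against.** The strongest reply is that the design already deals with regression to the mean. Controls are randomised, concurrent, selected on the same threshold and re-measured at the same point, so the artefact is equal in expectation in both arms and cancels from H2. That stands. A reader might infer that H2 cannot separate benefit from regression to the mean; the documents do not support this. Only a within-group reading is exposed, and no section says that a within-group change will be taken as efficacy.

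Second, this is a feasibility pilot meant to estimate effects, and it claims no power. That also stands: low power alone is not an error here, and ANCOVA does not rescue a 9% effect. The power figures show how much information the chosen endpoint throws away, not that the trial had to be larger.

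Third, Fisher's test is not named in the plan, and percent change, which is, would recover nearly all the power if compared between arms. This is correct, and it limits the case for ANCOVA over percent change to good practice. It does not supply the missing contrast, because the plan never says that percent change in blood levels will be compared between groups.

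Finally, the general sentence on inferential statistics, read with H2, implies some between-arm comparison. It does, but it leaves method, scale and covariates open.

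**Conclusion.** The point holds in this form: H2's any-decrease endpoint discards the size of change, no between-arm analysis is specified for IR, and the before/after wording of Aim 3 is open to regression to the mean of about 3-14% under the main assumptions.

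Two stronger readings should be resisted. H2 has very low power; it is not incapable of detecting a benefit (13% at a 30% reduction and 23% at 40% in the central case). And the plan is not without any between-arm intent, since H2 states one; what is missing is its specification for IR.

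Only the Fisher ceiling is free of HOMA-IR assumptions. Every other magnitude rests on SD, ICC and median values that the documents do not give. The direction is secure and the exact figures are not. This is a cheap improvement and a should-fix, not a fatal flaw.

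**What to change.** In the Objectives and the Analysis Plan, replace the any-decrease comparison and the blood-level sentence with text such as: End-of-intervention HOMA-IR will be compared between randomised groups by ANCOVA on log HOMA-IR, with log baseline HOMA-IR as covariate. The ratio of geometric means (SLEEP-Extend/control) will be reported with its 95% CI as an estimate.

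Then:
- keep the proportion with a decrease as a descriptive summary;
- reword Aim 3, or add a sentence, so that within-group changes are not read as intervention effects;
- if expected precision is stated, give it as a range with its assumptions (roughly ×0.75-1.33 to ×0.63-1.58 at 10 per arm), and acknowledge that a 9% effect is not realistically detectable at this size.

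A repeat draw before randomisation would reduce regression to the mean but is not needed for a valid randomised contrast.

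The cost is a few sentences and no new data. The downside is that IR becomes an estimate with a wide interval rather than a yes/no hypothesis.
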